11.0 Statistical/Data Analysis Plan

11.1 Statistical Considerations:

List the statistical methods to be used to address the primary and secondary objectives, specific aims, and/or research hypotheses. Explain how missing data and outliers will be handled in the analysis. The analysis plan should be consistent with the study objectives. Include any sub-group analyses (e.g., gender or age group). Specify statistical methods and variables for each analysis. Describe how confounding variables will be controlled in the data analysis

The statistical plans discussed below are not final or definitive. They will need to evolve as the flu seasons develop and we communicate with other ILI study centers and the sponsors. In case of

a severe epidemic, they may have to change substantially. Detailed statistical protocols will need to be created for the specific studies that will fulfill secondary objectives. The statistical considerations below for the secondary objectives will serve as starting points for the more detailed statistical plan.

Primary Aim

Specific Aim #1: Comparison of the effectiveness (prevention of laboratory-confirmed influenza illness) of three types of licensed seasonal influenza vaccines.

Research question: Is either the cell-culture based vaccine or the recombinant vaccine more effective than egg-based vaccine? There are two hypotheses of interest based on influenza attack rates (AR): Vaccine Effectiveness (VE)= $(\underline{AR}_0 - \underline{AR}_1) \times 100\% = (1-\underline{AR}_1/\underline{AR}_0) \times 100\% = (1-\underline{RR}) \times 100\%$

AR₀

when AR_0 is placebo, VE~= vaccine efficacy or via Nauta ("absolute vaccine efficacy") when AR_0 is the egg-based vaccine then the VE~= *relative* vaccine efficacy.

We want relative VE of 33% => $1 - AR_1/AR_{egg} = 0.33$, therefore 1- 0.33 = $AR_1/AR_{egg} = RR$ therefore 0.67 =RR (AR1 = attack rate in either cell-culture based or recombinant vaccine)

We have simplified the primary hypotheses for the study and have opted for two pairwise comparisons rather a single three-way comparison. There are two hypotheses of interest based on influenza attack rates (AR):

H₀: RR=1 vs H_A: RR < 1; alpha=0.025;

The RR to be tested is defined as: 1) RR1=AR_{cell} / AR_{egg} and 2) RR2=AR_{recombinant} / AR_{egg} Text: Statistics in Clinical Vaccine Trials by Jozef Nauta.

1. Endpoint:

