The ability of the study to detect a difference in effect is proportionate to the incidence of the outcome. A total of 172 influenza cases were reported among the 10,771 subjects enrolled in first three years of the study (2018-2021). The influenza attack rate has ranged from 0% in third season (COVID-19 pandemic), to 2.5% in the second season, with an overall attack rate 1.6% The observed attack rates are lower than baseline attack rates of 5% and 3% that formed the basis of sample size calculations for the first three years of the study. Consequently, the power to detect significant differences in VE between vaccine arms has been too low to due to the low attack rates. For the fourth year of the study is to increase the enrollment target from 15,000 to 18,00 to enhance power to detect significant differences in VE between attack rates are lower.

Secondary Aims:

Specific Aim #2:

Determine whether cell-culture-based and egg-based influenza vaccines give comparable HI and PVN titers to egg- and cell-matched vaccine antigens. An outcome of this objective is the potential to determine whether cell-culture-based vaccine antigens can provide broader coverage of circulating viruses than egg-based vaccine antigens.

Research Question: Is the proportion of subjects who seroconvert in either the cell-culture based or recombinant vaccine arm of the study greater than in the egg-based vaccine arm of the study.

There are two hypotheses of interest for Specific Aim 2, based on the seroconversion rates (SCR)

H₀: RR=1 vs H_A: RR < 1; p=0.025; The RR to be tested is defined as: 1) RR1=SCRcell / SCRegg and 2) RR2=SCRrecombinant / SCRegg

1. Endpoints:

- Humoral responses: HAI titer, anti-NA titer, virus-neutralizing titer
- Cellular responses (exploratory): frequency of antigen-specific CD4 and CD8 cells, B cells

SA 2.1: To obtain post-vaccination sera panels to determine breadth of reactivity to circulating strains.

This will be accomplished by recruiting consenting adults to an IRB-approved study conducted during a routine influenza vaccination campaign, collecting sera up to 30 days before and 21-35 days after vaccination with egg- or cell-culture-based or recombinant influenza vaccines. The samples will be de-identified and shipped to partner laboratories for aliquoting, storage, and antigenic analyses. We intend the study to be conducted during early vaccination campaigns performed at DoD facilities.

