11.5 Please provide a justification for your sample size

Main Study

Based on an alpha of 0.025 (1-sided) and a power of 0.80, a sample size of 18,000 (6,000 per arm) subjects has the power to detect a 33% difference in effectiveness between egg-based vaccine and two other vaccine preparations, assuming an influenza incidence of 2.3% in the egg-based arm and 1.54% in the cell-culture-based and recombinant arms. It assumes that 15% of subjects will be lost to follow-up.

Substudy

Based on an alpha of 0.025 (1-sided) and a power of 0.80, a sample size of 1,200 subjects (400/arm) has the power to detect a 22% relative difference in seroconversion rate if there is a 50% seroconversion at day 28 among the egg-based vaccine recipients. It assumes that 15-20% of subjects will be lost to follow-up.

11.6 Data Analysis Plan:

See section 11.1

12.0

Participant Information

12.1 Subject Population:

The study is comprised of DEERS-eligible adults (active duty, retirees and beneficiaries) vaccinated (at an MTF) (will be vaccinated) with one of the licensed egg-based, cell-culture-based or recombinant influenza vaccines during the 2018-2019, 2019-2020, 2020-2021, 2021-2022 influenza seasons in the United States. Subjects enrolled in the study during 2018-2019, 2019-2020, and/or 2020-2021 may also be enrolled in the 2021-2022 season.

12.2 Age Range:

Check all the boxes that apply. if the age range of potential subjects (specimens, records) does not match the range(s) selected, please specify in the text box.

0-17

- ✓ 18-24
- 25-34
- 35-44
- 45-54
- 55-64
- 65-74
- 75+

12.3 Gender:

- Male
- ✓ Female
- C Other

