3.2 Immunogenicity Sub-Study

Nested within this trial is an immunogenicity sub-study, in which 1,000 subjects will have their blood drawn prior to influenza vaccination and again at 21-35 days post-vaccination to assess changes in immune responses to the vaccines. Collection of a buccal swab for host genomic studies will be optional at enrollment or the 21-35 days post-vaccination visit.

	Recruits	Non-recruits	Non-recruits; Sub-Study
Consent and sociodemographic data collection	X	Х	Х
Sub-Study blood draw (pre-vaccination)			X
Vaccination with one of 3 vaccines	X	Х	Х
Weekly surveillance begins for non-recruits 14 days after vaccination		X	X
Sub-Study blood draw (post-vaccination)			X
ILIs - Visit 1 (if ILI is experienced) - nasopharyngeal swab, blood sample	X	X	X
ILI severity survey (if ILI is experienced)		Х	X
ILIs - Visit 2 (if ILI is experienced) - blood sample ~28d after Visit 1		X	X

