5.2.2 Endpoints

5.2.2.1 Relative risk for seroconversion

Relative risk of seroconversion among participants who received cellculture-based influenza vaccine (FlucelvaxR) as compared to those receiving egg-based influenza vaccine will be calculated using the following formula:

$$RR_{cell} = \frac{p_{cell}}{p_{egg}}$$

Where:

 p_{cell} = proportion seroconvert among the cell-culture-based influenza vaccination group

 p_{egg} = proportion seroconvert among the egg-based influenza vaccination group

and

Relative risk of seroconversion among participants who received recombinant HA (FluBlokR) influenza vaccine as compared to those receiving egg-based influenza vaccine will be calculated using the following formula:

$$RR_{recombinant} = \frac{p_{recombinant}}{p_{egg}}$$

Where:

 $p_{recombinant}$ = proportion seroconvert among the recombinant HA influenza vaccination group

 p_{egg} = proportion seroconvert among the egg-based influenza vaccination group

The proportion that seroconvert equals the number seroconvert (definition 3.1.2.3) divided by the number of vaccinated individuals that were enrolled in the Sub-Study and had the pre- and post-blood draws.

Confidence intervals (95%) will be calculated using the standard formulas for relative risk. The relative risk will be statistically significant if the p-value is less than or equal to 0.025 (one-sided test). The interim analysis for relative risk after the first influenza season uses a stricter p-value (<0.0001). Because of this, the final analysis will not need to adjust the p-value out of concerns about multiple looks.

Relative risk for seroconversion as defined in 5.2.2.1 will be evaluated for each vaccine-type (A/H1N1, B/Yamagata, B/Victoria, and A/H3N2);

5.2.2.2 Geometric Mean Titers (GMTs) – GMTs will be calculated pre- and post-vaccination. Non-inferiority will be based on a 2-sided test comparing post-vaccination GMTs between vaccine types.

5.2.2.3 Mean-Fold Rise – Ratios of participant post-vaccination titers divided by the pre-vaccination titers.

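### Aim 2 of the sub-study: the one-sided seroconversion test is printed in the wrong direction in Protocol 11.1, and GMT non-inferiority in the SAP has no margin or decision rule

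*Protocol*

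**What the plan says.** **Seroconversion.**
- In Protocol 11.1, Specific Aim 2, the research question is whether the proportion seroconverting in either newer-vaccine arm is "greater than in the egg-based vaccine arm of the study".
- The hypothesis line that follows sets the alternative as "RR < 1; p=0.025; The RR to be tested is defined as: 1) RR1=SCRcell / SCRegg", with the recombinant ratio defined in the same way.
- Protocol 9.4 has the same question, ratios and 0.025 level, but gives the alternative as RR>1.
- SAP 5.2.2.1 defines the same ratios and says "The relative risk will be statistically significant if the p-value is less than or equal to 0.025 (one-sided test"). It does not say which side. It also plans 95% confidence intervals for the relative risk.

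**Titers.**
- The aim itself is to determine whether the vaccines "give comparable HI and PVN titers to egg- and cell-matched vaccine antigens".
- SAP 5.2.2.2 says: "Non-inferiority will be based on a 2-sided test comparing post-vaccination GMTs between vaccine types". It gives no margin, significance level or interval for the GMT ratio, and neither document supplies them elsewhere.

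**Size and status.**
- Protocol 11.5 plans 1,200 subjects (400 per arm), one-sided alpha 0.025 and 80% power to "detect a 22% relative difference in seroconversion rate if there is a 50% seroconversion at day 28" in the egg-based arm, allowing 15% to 20% loss.
- SAP 3.2 describes a sub-study "in which 1,000 subjects will have their blood drawn prior to influenza vaccination".
- Protocol 11.1 says its considerations for the secondary objectives "will serve as starting points for the more detailed statistical plan".

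**The concern.** A one-sided test needs one direction, fixed before the data are seen. Here the protocol gives two opposite directions and the SAP gives none. Taken literally, the line in 11.1 tests whether the newer vaccines seroconvert fewer people than the egg-based vaccine, and such a test cannot confirm the benefit that the research question asks about.

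The GMT sentence raises a different problem. A two-sided test of equal GMTs does not establish non-inferiority. A non-significant difference may only reflect wide intervals, and a significant one may lie in either direction. Non-inferiority needs a margin and a statement that a particular confidence limit must clear it. Without these, whoever writes the report has to supply the rule, possibly with the GMTs already known. Because Aim 2 speaks of comparable titers, this analysis is a natural one to cite for that conclusion.

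**Working it through.** **1. Reproduce the planned size.** Inputs from Protocol 11.5: egg-based rate p0 = 0.50; 22% relative difference, so p1 = 0.50 × 1.22 = 0.61; one-sided alpha 0.025 (z = 1.96); power 0.80 (z = 0.842).

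Pooled-variance formula, with mean rate 0.555:

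n = [1.96·√(2·0.555·0.445) + 0.842·√(0.50·0.50 + 0.61·0.39)]² / 0.11² = 320 evaluable per arm.

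With 20% loss, 320/0.80 = 400 per arm, which is the protocol's figure. The same formula for 0.50 against 0.39 also gives 320, so the sample size does not reveal the intended direction and does not change when the sign is corrected.

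**2. Chance of rejecting in each direction when the truth is 0.61 against 0.50.** Unpooled standard error: se = √((0.25 + 0.2379)/n). Evaluable numbers per arm are 400 × 0.80 = 320 and 400 × 0.85 = 340 for the protocol's 1,200. For the SAP's 1,000 they are 333.3 × 0.80 = 267 and 333.3 × 0.85 = 283.

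- Alternative RR>1: Φ(0.11/se − 1.96)
- Alternative RR<1: Φ(−0.11/se − 1.96)

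| Total | Loss | Evaluable per arm | RR>1 | RR<1 |
|---|---|---|---|---|
| 1,200 | 20% | 320 | 80.4% | 8.9 × 10⁻⁷ |
| 1,200 | 15% | 340 | 82.7% | 5.8 × 10⁻⁷ |
| 1,000 | 20% | 267 | 73.0% | 2.9 × 10⁻⁶ |
| 1,000 | 15% | 283 | 75.5% | 2.0 × 10⁻⁶ |

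With the pooled variance under the null, the first two RR>1 figures become 80.1% and 82.4%, an immaterial difference. Each figure is for one pairwise comparison on one strain.

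**3. What the planned interval would show.** At 320 per arm, the expected 95% interval for RR is

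exp(ln 1.22 ± 1.96·√(0.50/(0.50·320) + 0.39/(0.61·320))) = 1.06 to 1.40.

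It excludes 1 on the favourable side whatever sign is printed for the test.

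**4. What GMT margin 320 per arm could support.** The documents give neither a margin nor a titer SD, so this is illustrative. Assume equal true GMTs, a deciding lower limit from a two-sided 95% interval, 80% power, and a log2-titer SD of 1.5 to 2.5. The tightest supportable margin on the new/egg GMT ratio is

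2^−[(1.96 + 0.842)·SD·√(2/320)]

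- SD 1.5: 0.79
- SD 2.0: 0.74
- SD 2.5: 0.68

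These values show what the sub-study could resolve. They do not justify any particular margin.

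**The case against.** The strongest reply is that the sign is a clerical slip with only one sensible reading. The question beside it asks for an increase, 9.4 prints RR>1, and the RR<1 form is correct for Aim 1, where attack rates should fall, so it was probably carried over. Nobody appears to intend a test for lower seroconversion. Moreover, a two-sided 95% interval for RR lying wholly above 1 is, apart from the choice of variance formula, the same decision as a one-sided 0.025 test for RR>1. This largely stands: the practical damage from the sign is small. It does not make the text correct, since two opposite alternatives are on record and the SAP, which should settle the matter, is silent.

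A second reply is that Protocol 11.1 calls its plans provisional and expects separate detailed statistical protocols for the secondary objectives, so a margin may be set in a document not available here. That is possible, and it cannot therefore be said that a rule will be chosen after the data are known. But the SAP supplied covers this sub-study, introduces the non-inferiority claim itself and leaves the rule blank.

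A third reply is that both protocol hypotheses for Aim 2 concern seroconversion, and GMT non-inferiority rests on one SAP sentence. That limits its weight. It also makes it easy either to complete or to drop.

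**Conclusion.** Both points hold and should be corrected before the sub-study is analysed. The direction error changes neither sample size nor estimation. Its effect is on the formal test: 80.4% to 82.7% power as intended with 1,200 subjects, against a rejection probability below 0.000003 if 11.1 is followed literally. These figures rest on the protocol's own rates and losses and on a normal approximation.

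The GMT sentence is the more substantive gap, because as written it cannot support a non-inferiority conclusion and no other planned interval stands in for the missing rule. The margins shown depend wholly on assumed SDs.

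The two documents also disagree on sub-study size. At the SAP's 1,000, power for RR>1 is 73.0% to 75.5%, below the stated 80%. The primary endpoint is not touched by any of this.

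**What to change.** - **Protocol 11.1:** change the Aim 2 alternative to RR>1, in line with its research question and with 9.4.
- **SAP 5.2.2.1:** state that the one-sided test is for RR>1.
- **SAP 5.2.2.2:** choose one of two courses. Either drop the non-inferiority label and report the new/egg GMT ratio with a 95% interval for each strain, or keep it and claim non-inferiority only when the lower limit of the two-sided 95% interval for that ratio exceeds a margin fixed and justified before analysis. Say explicitly that the comparison is between vaccine products, because SAP 5.1.3 uses the term vaccine type for strains.
- **Sub-study size:** reconcile 1,200 (Protocol 11.5) with 1,000 (SAP 3.2) and state power on the figure kept.
- **Optional, for precision only:** estimate the GMT ratio by ANCOVA of log post-vaccination titer on arm and log pre-vaccination titer. The variance factor is 1 − r², so an assumed pre/post correlation of 0.4 to 0.6 would lower the variance by 16% to 36%.

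The cost is wording in the protocol and SAP. No further participants, samples or assays are needed.

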 - Number of days hospitalized (if hospitalized for care)
- Number of work/duty days absent related to ILI episode

Visit #2- Convalescent Visit (21-35 post trigger)

In-clinic self-collected blood sample (40 μ L) or intravenous blood draw (16 mL) (subject's choice, consistent with the first visit, if possible)

- If hospitalized
 - ILI hospitalization status
 - $^{\circ}$ Number of days hospitalized (if hospitalized for care)
- Total number of work/duty days absent related to ILI episode

ILI Healthcare utilization and costs

Data on health care utilization and costs attributed to ILI episode will be abstracted from the MDR at the end of each influenza season.

Deviations:

Missed nasal specimens (in-person and/or self-collected) and self-collected blood samples (in-person and/or self-collected) will be considered protocol deviations

Collection of the Human Biological Specimens/Specimen processing: *Blood:*

- All subjects who develop ILI during the current influenza season will provide specimens as part
 of the acute ILI visit and convalescent ILI visit . Recruits/trainees with an ILI will not be
 required to provide convalescent blood samples. Blood may be collected via venipuncture in
 clinic (16 mL per timepoint) or with a Mitra kit (40 µL per timepoint). Up to 16 mL will be
 collected at each of these visits; up to 96 mL total over the course of follow up.
- Subjects may opt-in for a day of vaccination and post vaccination self-collected blood sample (40 μL per timepoint).
- *Immunogenicity substudy subjects only*. Subjects in the substudy will undergo phlebotomy up to 30 days prior to vaccination and again 21-35 days post-vaccination to assess changes in humoral and cell-mediated immunity in response to influenza vaccination. Approximately 40

mL will be collected at each of these two visits and the end of study self-collected blood sample; approximately 80 mL over the course of the study. A sample of the stored serum samples will be shipped to the FDA CBER, or other partner, laboratories for analysis. Subjects who participate in the substudy will not be selected to provide the optional same-day/post-vax blood samples.

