SA 2.2: To identify individuals who responded to H1N1, H3N2, B/Victoria and B/Yamagata vaccine components. This will be accomplished by testing pre- and post-vaccination sera for HA inhibition (HI) and pseudovirus microneutralization (PVN) antibody titers. Individuals who had a 4-fold or greater response against each matched antigen in the vaccine will be considered responders (i.e. if egg-based vaccine, the test will be conducted against egg-based antigen). The study will be designed to identify responders to egg- and cell-culture-based vaccines for each vaccine antigen (H1N1, H3N2, B/Yamagata and B/Victoria). For H3N2 strains that do not hemagglutinate, only PVN titers will be determined. The sera collected postvaccination from responders will be aliquoted and distributed to laboratories performing assays to evaluate the breadth of antibody reactivity.

SA 2.3: To evaluate differences in serum reactivity between egg- , cell-culture-based and recombinant antigens.

We will test pre- and post-vaccination sera against antigens with sequences corresponding to the "other" platform. We will compare PVN antibody titers against egg- and cell-culture-based antigens for all strains included in the vaccine, and calculate the response rate (i.e. percent of individuals in each arm with a 4-fold or greater titer response) of each arm of the study against egg and cell antigens. The results from this test will indicate whether antibodies elicited in response to egg- and cell-culture-based vaccines are specific for the immunogen.

SA 2.4: Compare the breadth of the antibody response elicited by egg, cell-culture-based and recombinant vaccines to circulating strains.

To determine the breadth of antibody reactivity, post-vaccination serum PVN titers will be measured against cell-culture-based vaccine and emerging circulating virus antigens representing most clades from each subtype. Only cell-based sequences will be used in this analysis because these are representative of the original human isolate sequences. We

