propose to include the HAs of at least 6-10 recent virus isolates per subtype/lineage. PVN titers against recent virus isolates that are >4 fold different from the homologous vaccine antigen will be considered low reactors (LRs). The breadth of reactivity will be scored by calculating the number of LRs identified for each study subject, e.g., sera that react to all antigens will be given a score of 100%, sera that react to no antigens will be given a score of 0% and sera that react to 4 of 10 antigens will be given a score of 40%. The overall breadth of reactivity for each study Arm will be calculated as the average breadth of reactivity for all persons in the Arm. If the difference between the groups is not significant, additional antigens within the subtype/lineage but that are known to be antigenically-distinct, may be tested.

SA 2.5: To examine the breadth of reactivity against past strains.

Recent studies demonstrate a back-boost effect following vaccination, i.e. increased antibody titers against influenza antigens from past vaccines or infections. The human immune responses are therefore impacted by prior vaccination history or infection. To retain the possibility of performing additional tests that examine the back-boost effect, left over sera will be stored for future additional investigations of how pre-existing breadth of antibody reactivity to past influenza strains influences responses to current influenza vaccines.

Exploratory Aims:

Specific Aim #3: To determine if the impact of the influenza vaccine on disease burden and the attributable healthcare costs differs by product type.

An analysis of the impact of ILI and SARI on health care utilization will allow a more detailed estimation of the burden of infections caused by these pathogens in military populations. The collection and analysis of health care utilization information will be useful for informing priorities for ARI control and will serve as a basis for the comparison of the effectiveness of different ILI control measures to enhance Force Health Protection.

Endpoints:

- Incidence of PCR-confirmed influenza cases
- Frequency of influenza-confirmed hospitalization
- Frequency of influenza-like illness
- Work days lost due to influenza
- Work days lost due to influenza-like illness
- · Healthcare costs/utilization attributable to influenza
- · Healthcare cost/utilization attributable to influenza-like illness

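### SA 2.4 lets antigens be added only after a non-significant breadth comparison, and SA 2.2 and SA 2.4 disagree on whose sera enter the breadth assays

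*Protocol*

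**What the plan says.** **Adding antigens.** Protocol 11.1, SA 2.4, scores each post-vaccination serum against at least 6-10 recent isolates per subtype or lineage. An isolate counts as a low reaction when its titer differs more than 4-fold from the titer to the homologous vaccine antigen. After the arm averages are described, the text adds: "If the difference between the groups is not significant, additional antigens within the subtype/lineage but that are known to be antigenically-distinct, may be tested". It names no test, significance level, list or maximum number of added antigens, or limit on rounds. It also gives no rule for reporting the first result beside the extended one. SAP 5.2.2 covers seroconversion, GMT and mean-fold rise; breadth does not appear.

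**Whose sera.** SA 2.2 states: "The sera collected postvaccination from responders will be aliquoted and distributed to laboratories performing assays to evaluate the breadth of antibody reactivity". SA 2.4 states: "The overall breadth of reactivity for each study Arm will be calculated as the average breadth of reactivity for all persons in the Arm". Nothing reconciles the two.

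**Which antigen.** Under SA 2.2, response is a 4-fold or greater rise against the arm's own matched antigen ("i.e. if egg-based vaccine, the test will be conducted against egg-based antigen"). Under SA 2.4, breadth is scored differently: "Only cell-based sequences will be used in this analysis because these are representative of the original human isolate sequences".

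**The concern.** The extension rule works in one direction. A significant first comparison stands, while a non-significant one may be extended with antigens chosen because they are antigenically distinct. If the extended data are then tested for a difference, the arms get a second chance only when the first has failed. A difference found that way is weaker evidence than its p-value suggests.

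The second issue is the population. Responder status is measured after randomisation and can be affected by the vaccine. The filter also differs by arm: an egg recipient qualifies on egg antigen, yet is scored for breadth on cell-based sequences. A responders-only comparison asks how broad the response is among those who responded to their own vaccine. An all-persons comparison asks how broad it is among those vaccinated. SA 2.4 is where the arms are compared on breadth against circulating strains, so a reader needs to know which question was answered.

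**Working it through.** **1. The plan's own figure.** The documents give no sample size for breadth. The sub-study figure in Protocol 11.5 is for seroconversion: 50% against 61% (50% x 1.22), one-sided 0.025, power 0.80.

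n per arm = [1.96 x sqrt(2 x 0.555 x 0.445) + 0.842 x sqrt(0.50 x 0.50 + 0.61 x 0.39)]^2 / 0.11^2 = 320 after rounding up. Allowing for 20% loss, 320/0.80 = 400. The stated 400 per arm reproduces, so sample size is not at issue.

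**2. Error rate if the added antigens are used to re-test.** From SA 2.4: first panel n = 6 to 10. Assumed: one-sided alpha 0.025 (borrowed from seroconversion); one addition of k = 2 to 10 antigens with k no larger than n; a common correlation rho = 0.2 to 0.6 between antigen scores in one serum.

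- Variance of a panel mean: v(m) = (1 + (m-1) rho)/m.
- Correlation of the first test with the pooled re-test: sqrt(v(n+k)/v(n)).
- Correlation of the first test with the new antigens alone: rho/sqrt(v(n) v(k)).
- Error = 1 - P(Z1 < 1.96 and Z2 < 1.96), bivariate normal.

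Example with n = 8, k = 4, rho = 0.2: v(8) = 0.300, v(12) = 0.267, v(4) = 0.400. The pooled correlation is 0.943, giving an error of 3.3%. The new-antigens-alone correlation is 0.577, giving 4.4%.

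| Re-test | Lowest error | Highest error |
|---|---|---|
| Pooled panel | 2.7% (n=10, k=2, rho=0.6) | 3.5% (n=6, k=6, rho=0.2) |
| New antigens alone | 3.3% (n=10, k=10, rho=0.6) | 4.6% (n=6, k=2, rho=0.2) |

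If the correlation between the two panels is instead set directly, from 0.9 down to 0, the error is 3.0-4.2% pooled and 3.5-4.9% alone. These rates are per subtype and per pairwise comparison. No limit on rounds is stated; the extreme of fully independent tests gives 1 - 0.975^3 = 7.3% for three.

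**3. Shift in the arm difference if only responders are assayed.** Let m(p) be the mean of a standard normal above its upper-p cut: m(0.50) = 0.798, m(0.61) = 0.629. Let rho now be the correlation of breadth with response in the non-egg arm, assumed 0.2 to 0.5, and c the egg-arm correlation as a fraction of it. Shift (non-egg minus egg, in SD units) = rho x [m(p1) - c x 0.798], with the egg arm at 50% responders.

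| Non-egg responders p1 | c = 1 | c = 0.9 | c = 0.6 |
|---|---|---|---|
| 61% | -0.03 to -0.08 | -0.02 to -0.04 | +0.03 to +0.08 |
| 50% | 0 | +0.02 to +0.04 | +0.06 to +0.16 |
| 70% | -0.06 to -0.15 | -0.04 to -0.11 | 0.00 to +0.01 |

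The shift is zero if breadth is unrelated to response. For scale, with 320-340 evaluable per arm, responders number 160-170 (egg) and 195-207 (61% arm). The standard error is then sqrt(1/160 + 1/195) = 0.107 SD, or 0.104 SD at the larger counts. Most entries are below that; the extremes (+0.16, -0.15) are about one and a half times it. The sign changes with c and p1.

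**The case against.** The strongest reply is that the protocol says only that further antigens may be tested, which describes laboratory work. It does not say that the results are pooled, re-tested at the same level, or used to claim a difference. Aim 2's formal hypotheses concern seroconversion, and no alpha is set for breadth. A reader might infer that the plan builds in an inflated false-positive rate; the documents do not go that far, and the inflation holds only if the added data are used to re-test. What stands is that the trigger depends on the first result and that nothing excludes this use.

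Protocol 11.1 also calls its plans provisional and says detailed statistical protocols for the secondary objectives are still to be written. That explains the missing alpha and antigen list and lowers the severity. But the same paragraph makes the present text the starting point, so the trigger would carry forward unless changed.

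On the sera, the responder sentence sits under SA 2.2 and could concern only the distribution of reference panels. A responders-only comparison between arms is nowhere stated, and a reader who infers that one is planned goes beyond the text. Because the SA 2.2 sentence names the breadth assays, clarification is still needed. One might also count Protocol 10.1 ("A sample of the stored serum samples will be shipped to the FDA CBER, or other partner, laboratories for analysis") as a third conflicting statement. It is a general shipping sentence that does not mention breadth and may refer to aliquots, so the point does not rely on it.

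Finally, restricting to responders may have a practical reason. If titers below 10 are recorded as 5 (an assumption; no limit is given for the neutralization assay), a homologous titer of 20 can fall at most 20/5 = 4-fold, which is not more than 4-fold. Such a serum would score as fully broad. This objection stands and is taken into the fix.

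**Conclusion.** The concern holds in limited form and should be corrected. SA 2.4 has a result-dependent rule for extending the antigen panel, without alpha, cap or exploratory label. If it leads to a re-test at an assumed one-sided 2.5%, one addition gives an error of roughly 3-5%. Neither end of that range can be preferred: scoring the same sera raises the correlation between panels, while choosing antigenically distinct antigens lowers it.

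SA 2.2 and SA 2.4 also need reconciling. If only responders are assayed, the randomised comparison is lost. A reader might infer a large or predictable bias; the calculation supports neither, because the direction is unknown and the size is probably below one standard error. The changed question is the main consequence.

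The alpha, correlations, number of added antigens and responder rates used for breadth are all assumptions. The impact is minor, confined to one secondary sub-aim, and the primary endpoint is unaffected.

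**What to change.** - Delete the non-significance trigger. Fix the antigen panel for each subtype before titers are compared by arm, and report any later antigens as exploratory beside the first result, whatever that result was.
- Reconcile SA 2.2 and SA 2.4. Base the between-arm breadth comparison on all sub-study participants with both draws, which is the set SAP 5.2.2.1 already uses for seroconversion ("the number of vaccinated individuals that were enrolled in the Sub-Study and had the pre- and post-blood draws"), or on a random sample of them within arm. Keep responders-only as a supportive analysis.
- State in advance how sera with homologous titers near the assay limit are scored. This matters for low-titer responders as well as non-responders.
- Put these rules in the detailed secondary-objective plan that Protocol 11.1 says is still to come.

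**Cost.** Protocol wording and a short breadth section. Some non-responder sera would be assayed, and low-titer sera need the scoring rule. Testing everyone means 1,200 x 0.80 to 0.85 = 960-1,020 sera per subtype with the enrolment in Protocol 11.5, or 800-850 with the 1,000 in SAP 3.2. Responders only, at assumed rates of 50/61/61% and 1,200 enrolled, would be about 550-585 (320 to 340 x 1.72). A random sample of that same size needs no extra assays.
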